**STUDY SYNOPSIS**

Protocol Number	SKM16-LYT-MEL Amendment 1
Protocol Title	Randomized, Double-blinded, Split-face Study comparing the Cosmetic Efficacy and Tolerability of Two Topical Products in Subjects with Moderate Facial Melasma
Study Duration	3 months (12 Weeks)
Study Population	20 healthy subjects with Fitzpatrick Skin Types III-VI
Objectives	To evaluate and compare the efficacy and tolerability of two topical products in the improvement of facial melasma
Study Design	Single site, investigator-initiated, double-blinded, parallel arm, randomized treatment, split-face, 12-week study comparing the efficacy and tolerability of SkinMedica's cosmetic topical brightener versus generic hydroquinone 4% topical prescription cream. A total of 20 healthy subjects will be enrolled into this study. Subjects will be screened and randomized at Baseline and will return for visits at Weeks 4, 8 and 12. The test products will be applied only to the affected areas (dark patches) twice a day, morning and evening, every day for 12 weeks. Ancillary products will be provided for basic daily skincare regimen use.
Study Products	
 
• SkinMedica Facial Cleanser
 
• SkinMedica Rejuvenative Moisturizer
 
• SkinMedica Essential Defense Mineral Shield Broad Spectrum SPF 35 Sunscreen
 
• Test Product A (Lytera 2.0)
 
• Test Product B (4% Hydroquinone Topical Cream)
 

Eligibility Criteria	Subjects aged 18+ [REDACTED] with symmetrical moderate facial melasma.

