#### **4.4 Treatment Group Randomization**

Subjects will be randomized in a 1:1 fashion to receive treatment with SkinMedica's cosmetic topical brightener or 4% hydroquinone. A randomization table will be provided by the sponsor and used to determine which facial side will be treated with Test Product A (cosmetic topical serum "Lytera 2.0") and Test Product B (4% hydroquinone) for each subject.

- Randomization and distribution of study products by the Unblinded study staff

[REDACTED]

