#### **Melasma Severity Rating Scale:**

At the screening/baseline visit and the end of treatment visit (week 12), the Investigator will assess the subject's facial skin for the severity of symmetrical facial melasma using the following Melasma Severity Rating Scale on the left and right facial sides. Subjects must present with a score of 2 for the left and the right facial sides to be enrolled into the study.

Score	Hyperpigmentation Status
0	Cleared: color of melasma lesions approximately equivalent to surrounding normal skin or with minimal residual hyperpigmentation
1	Mild: color slightly darker than the surrounding normal skin
2	Moderate: color moderately darker than the surrounding normal skin
3	Severe: color markedly darker than the surrounding normal skin

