**Half-face Evaluation of Melasma Area Severity Index (MASI) Score**

At all visits, (baseline, weeks 4, 8 and 12), the Investigator will assign a grade for the left and right facial sides, for each of the below units, for the variable A (percentage of each area involved), D (darkness of pigment) and P (pattern of involvement), as described in detail below.

Calculations will be conducted by the sponsor upon receipt of the completed CRFs.

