## **7.0 STATISTICS**

Statistical analyses will be conducted by the sponsor on an intent-to-treat basis (ex: all enrolled subjects, with at least one follow-up visit, will be included in the analysis).

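### Does calling this split-face trial parallel arm, with no paired analysis named in Section 7.0, put the product comparison at risk?

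*Combined protocol and SAP*

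**What the plan says.** The title in the Amendment 1 synopsis is "Randomized, Double-blinded, Split-face Study comparing the Cosmetic Efficacy and Tolerability of Two Topical Products", with no mention of parallel arms. The Study Design row of the same synopsis reads "Single site, investigator-initiated, double-blinded, parallel arm, randomized treatment, split-face, 12-week study" and sets the size: "A total of 20 healthy subjects will be enrolled into this study".

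Section 4.4 begins "Subjects will be randomized in a 1:1 fashion to receive treatment with" the brightener or 4% hydroquinone. Its next sentence says that a sponsor-supplied table is "used to determine which facial side will be treated with Test Product A" and which side gets Product B, subject by subject.

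Section 6.1 works by side throughout. For the Melasma Severity Rating Scale, "Subjects must present with a score of 2 for the left and the right facial sides to be enrolled into the study". For half-face MASI, "the Investigator will assign a grade for the left and right facial sides".

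Section 7.0 is one sentence. It states an intent-to-treat basis, explained as meaning that "all enrolled subjects, with at least one follow-up visit, will be included in the analysis". It gives no test, model, contrast or use of baseline, and it carries no redaction mark. Text after Section 4.4 is redacted.

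**The concern.** A parallel-arm trial and a split-face trial call for different standard errors. In the first, treatment groups contain different people and are independent. In the second, each person supplies one side to each product, and the comparison is made within the person. The protocol uses both labels in one phrase, and the opening of Section 4.4 reads as allocation of a subject to a single product. Section 7.0 does not settle the question, because it never says that products are compared within subjects.

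If the parallel-arm wording guided the analysis, 20 left and 20 right sides might be treated as 40 independent units. When the sides of a face are positively correlated, the standard error would be overstated, the confidence interval would be too wide and power would be lost. Positive correlation is likely here, since Section 3.1 requires symmetrical melasma and Section 6.1 requires the same severity score on both sides at entry. With 20 subjects, the loss could decide whether a moderate difference between products is detected. Baseline handling is also unstated. Only the 0-3 severity rating is fixed at entry, so half-face MASI may differ between sides at the start.

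**Working it through.** **Which design do the passages describe?**

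- Title: split-face only.
- Synopsis, Study Design: both labels.
- Section 4.4, first sentence: 1:1 between products, with the subject as the unit.
- Section 4.4, second sentence: both products in every subject, with sides set by the table.
- Section 6.1: the severity rating, overall hyperpigmentation, half-face MASI and global improvement are each scored for left and right.
- Sections 6.3 and 6.4: MELASQOL at Week 12 and the self-assessment questionnaires ask about each side.

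A literal parallel-arm reading cannot be squared with the second sentence of Section 4.4 or with Section 6.1. The split-face reading fits everything except two words in the synopsis and the *or* in Section 4.4. Even the 1:1 sentence can be defended. The table makes one draw per subject, A-left/B-right or the reverse, and the second side follows from the first. In that sense subjects are indeed randomised 1:1.

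**Does any figure in the plan depend on the label?** The only figure is the total of 20 subjects. The visible text gives no alpha, power, effect size, SD or correlation for it. It cannot be reproduced under either label, and nothing needs numerical correction.

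**What would the mistake cost if someone made it?** All inputs except n = 20 are assumptions: two-sided alpha 5%, per-side SD 1, true difference 0.6 SD, left/right correlation ρ of 0, 0.3, 0.5 and 0.8.

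- Paired: standard error √(2(1−ρ)/20), 19 df, power from the noncentral t. At ρ = 0.5 the standard error is √(1/20) = 0.224, the noncentrality is 0.6/0.224 = 2.68 and power is 72%.
- Unpaired on 20 + 20 sides: assumed standard error √(2/20) = 0.316, 38 df. Type I error and power come from 1,000,000 simulated sets at each ρ.
- 95% CI half-width at the true SD: unpaired 2.024 × 0.316 = 0.64; paired at ρ = 0.5, 2.093 × 0.224 = 0.47.

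| ρ | 0 | 0.3 | 0.5 | 0.8 |
|---|---|---|---|---|
| Power, paired | 44% | 58% | 72% | 98% |
| Power, unpaired | 46% | 45% | 44% | 42% |
| True type I error, unpaired | 5.0% | 2.1% | 0.75% | 0.015% |
| CI half-width, paired (SD) | 0.66 | 0.55 | 0.47 | 0.30 |
| CI half-width, unpaired (SD) | 0.64 | 0.64 | 0.64 | 0.64 |
| Detectable at 80% power, paired (SD) | 0.93 | 0.78 | 0.66 | 0.42 |
| Detectable at 80% power, unpaired (SD) | 0.91 | 0.87 | 0.84 | 0.78 |

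A separate run with 200,000 simulations agrees closely; at ρ = 0.5 it gives unpaired power 44% and type I error 0.7%.

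**Does the quoted wording lead to that mistake?** Taken literally, parallel arms would mean 10 subjects against 10 (18 df), with a detectable difference of 1.32 SD. That layout is impossible when every subject receives both products. The 20 + 20 analysis priced in the table is a different error, and no section asks for it.

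**The case for a change.** The strongest reply is that Section 7.0 is silent, shows no redaction and has no separate SAP text beside it, while two places use parallel-group language. Within-subject precision is the main statistical gain of a split-face design, and 20 subjects leave little to spare. Hydroquinone is called the gold standard in Section 1.0. If a non-significant result were read as comparability, a needlessly wide interval could hide a real difference. The correction would take only a few words and no new data.

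Much of this is factually right. The quotations are accurate, Section 7.0 names no method, and the power figures reproduce. What does not follow is the harm. Silence on the test is not an instruction to ignore pairing, and the design and data are organised by side from allocation to grading. The visible text makes no claim of comparability, so that risk is conditional. With complete pairs, the mean difference between sides is the same number whether or not pairing is used; only its standard error changes, and in the cautious direction.

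The missing baseline rule is likewise a choice among valid options, since both a change score and an adjusted side difference are sound. Writing a method in is not automatically safer. A mixed model over Weeks 4, 8 and 12 with a subject effect alone ignores the correlation between repeated readings of the same side. Two sets of null simulations put its type I error for the visit-averaged contrast at about 5%, 12%, 20-21% and 27-29% when the side-specific share of within-subject variance is 0, 25, 50 and 70%.

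Section 7.0 also names no primary endpoint or hypothesis. That is a wider matter than the parallel-arm label and is not decided here.

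**Conclusion.** The concern is accurate about the wording but does not call for a change. *Parallel arm* in the synopsis and *or* in Section 4.4 are loose drafting in a trial whose title, side allocation and side-by-side grading identify it as split-face. Comparing the products within subjects is what a competent analyst would do with these data, and nothing in Section 7.0 points the other way.

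If the pairing were ignored, the cost at a 0.6 SD difference would run from nothing at a correlation of 0 (46% unpaired against 44% paired) to a fall from 98% to 42% at 0.8, with type I error below the nominal 5% at every positive correlation shown. These figures rest on an assumed alpha, SD, correlation and effect, none of them in the documents, and they describe an analysis that the documents do not propose. The conclusion rests on the visible text only; the redacted material after Section 4.4 could not be read.

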**1.0 BACKGROUND**

Melasma is a common disorder of hyperpigmentation which typically presents as brown or grayish brown macules on the face, including the forehead, malar region, upper lip and chin. Melasma is commonly observed in women with Fitzpatrick skin types III to V (1), especially Asian and Hispanic women, although all skin types can be affected.

Contributing causes of melasma may include ultraviolet irradiation, oral contraceptives, hormone replacement therapy, pregnancy, and thyroid dysfunction (2) however the exact etiology are not yet fully understood.

Many patients find the uneven skin tone appearance caused by melasma to be cosmetically unacceptable. Finding a successful treatment remains challenging and frustrating. Therapies include broad-spectrum sunscreens, hydroquinone, tretinoin, kojic acid, alpha hydroxy acids, salicylic acid, and chemical peels.

The treatment of hyperpigmentation associated with skin aging and melasma is challenging due to the prolonged time to respond and its high relapse rate when therapy is discontinued. Patients are also required to avoid sunlight to improve therapeutic results. Hydroquinone is currently the gold standard for the topical treatment of hyperpigmentation and melasma.

## 2.0 STUDY OBJECTIVE

The objective of this study is to evaluate the efficacy and tolerability of SkinMedica's cosmetic topical brightener versus 4% hydroquinone in the improvement of the appearance of moderate facial melasma over the course of 12 weeks.

## 3.0 STUDY POPULATION

Twenty (20) healthy subjects presenting with symmetrical moderate facial melasma, who meet all inclusion and exclusion criteria will be eligible to participate in this study.

### 3.1 Inclusion Criteria

A subject will be eligible to participate if they meet all of the following inclusion criteria:

1. Female or male aged 18+ years [REDACTED]
2. Individuals with symmetrical (with at least left and right malar region involvement) moderate melasma [REDACTED].
3. Individuals that are willing to provide written informed consent and are able to read, speak, write, and understand English.
4. Individuals willing to sign a photography release.
5. Willing to withhold all facial treatments during the course of the study including botulinum toxin, injectable fillers, microdermabrasion, IPL, peels, facials, waxing, laser treatments and tightening treatments. Threading is allowed but not facial laser hair removal.

6. Willingness to cooperate and participate by following study requirements for the duration of the study and to report any changes in health status or medications, adverse event symptoms, or reactions immediately.
7. Willingness to not begin using any new cosmetic facial make-up during the study. If regular users of cosmetic facial make-up, they must have used the product(s) without any tolerability issues for at least 2 weeks prior to starting the study.
8. Willingness to avoid as much as possible, direct and prolonged sun exposure for the duration of the study (including tanning beds), especially from 10 AM to 2 PM. Subjects are asked to wear protective clothing prior to and during exposure. Any extended sun exposure must be recorded in the source documents.

### **3.2 Exclusion Criteria**

A subject will not be eligible to participate if they meet any of the following exclusion criteria.

1. Individuals diagnosed with known allergies to study provided skin care products.
2. Individuals who are nursing, pregnant, or planning to become pregnant during the study according to subject self-report.
3. Individuals with a history of skin cancer.
4. Individuals having a health condition and/or pre-existing or dormant dermatologic disease on the face (e.g., psoriasis, rosacea, acne, eczema, seborrheic dermatitis, severe excoriations etc.) that the Investigator or designee deems inappropriate for participation or could interfere with the outcome of the study.
5. Individuals with a history of immunosuppression/immune deficiency disorders (including HIV infection or AIDS) or currently using immunosuppressive medications (e.g., azathioprine, belimumab, cyclophosphamide, Enbrel, Imuran, Humira, mycophenolate mofetil, methotrexate, prednisone, Remicade, Stelara.) and/or radiation as determined by study documentation that the Investigator or designee deems inappropriate for participation or could interfere with the outcome of the study.
6. Individuals with an uncontrolled disease such as asthma, diabetes, hypertension, hyperthyroidism, or hypothyroidism. Individuals having multiple health conditions may be excluded from participation even if the conditions are controlled by diet, medication, etc.
7. Individuals with any planned surgeries and/or invasive medical procedures during the course of the study.

8. Individuals who are currently participating in any other facial usage study or have participated in any clinical trial within 4 weeks prior to inclusion into the study.
9. Individuals who have observable suntan, scars, nevi, excessive hair, etc. or other dermal conditions on the face that might influence the test results in the opinion of the Investigator or designee.
10. Individuals who started hormone replacement therapies (HRT) or hormones for birth control less than 3 months prior to study entry or who plan on starting, stopping, or changing doses of HRT or hormones for birth control during the study.
11. Individuals who used any of the following medications or had any of the listed procedures within the listed time frame prior to the study start date:
  - Retin-A®, Retin-A Micro®, Renova®, Avita®, Tazorac®, or Differin® within 3 months
  - Had a light-depth chemical peel or microdermabrasion within 1 month
  - Had a medium-depth chemical peel, medium-depth microdermabrasion, any systemic steroids, non-ablative laser, light and/or radio frequency or fractional laser resurfacing of the face and neck within 3 months
  - Any systemic retinoid (e.g. Soriatane®, Accutane®, Roche Dermatologics) within 12 months
  - Any topical or systemic antibiotics, such as minocycline, or any other known medications that can cause photosensitivity, such as hydrochlorothiazide, lasix, amiodarone, within 1 month
  - Any topical tretinoin product or derivative, imiquimod, 5-fluorouracil, or diclofenac on their face within 3 months
  - Prescription strength skin lightening products (e.g. 4% hydroquinone, tretinoin, AHA, BHA and polyhydroxy acids, 15% or 20% azelaic acid, 4-hydroxyanisole alone or in combination with tretinoin, etc.) within 3 months
  - Any non-prescription cosmetic anti-wrinkle, skin lightening products, or any other product or topical or systemic medication known to affect skin aging or dyschromia (products containing alpha/beta/poly-hydroxy acids, vitamin C, soy, Q-10, hydroquinone; systemic or licorice extract (topically), Tego® Cosmo C250, gigawhite, lemon juice extract (topically), emblica extract, etc.) within 2 weeks
  - Have undergone plastic surgery, Dermabrasion (deep skin peel), a deep chemical peel or ablative laser resurfacing of the face and neck within 12 months
  - Had facial treatment with a botulinum toxin base injectable (Botox), injectable fillers, or a fat transfer within 6 months

## 4.0 METHODS AND MATERIALS

### 4.1 Study Products

SkinMedica Facial Cleanser: Water/Aqua/Eau, Disodium Laureth Sulfosuccinate, Cocamidopropyl Hydroxysultaine, Sodium Lauryl Sulfoacetate, Camellia Oleifera Leaf Extract, Glycerin, Panthenol, Butylene Glycol, Ethylhexylglycerin, PEG-150 Pentaerythrityl Tetrastearate, PEG-6, Caprylic/Capric, Glycerides, Disodium EDTA, Phenoxyethanol, Parfum/Fragrance, Blue 1 (CI 42090), Yellow 10 (CI 47005)

Test Product A (Cosmetic topical serum “Lytera 2.0”): Water/Aqua/Eau, Butylene Glycol, Glycerin, Niacinamide, Polyacrylate-13, Phenylethyl Resorcinol, Tranexamic Acid, Vitis Vinifera (Grape) Flower Cell Extract, Plankton Extract, Tetrapeptide-30, Artemisia Capillaris Flower Extract, Vibrio Alginolyticus Ferment Filtrate, Alteromonas Ferment Extract, Tocopheryl Acetate, Polyisobutene, Polysorbate 20, Caprylic/Capric Triglyceride, Hydroxyacetophenone, Phytic Acid, Diethylhexyl Syringylidenemalonate, Disodium EDTA, Ethylhexylglycerin, Phenoxyethanol

SkinMedica Rejuvenative Moisturizer: Water/Aqua/Eau, Caprylic/Capric Triglyceride, Tocopheryl Acetate, Diglycerin, Isostearyl Behenate, Glyceryl Stearate, PEG-100 Stearate, Tetrahexyldecyl Ascorbate, Butyrospermum Parkii Butter, Panthenol, Phytosterols, Tocopherol, Tocotrienols, Squalene, Oryza Sativa Bran Cera, Aloe Barbadensis Leaf Juice, Algae Extract, Bisabolol, Ginkgo Biloba Leaf Extract, Avena Sativa Kernel Extract, Sodium Hyaluronate, Stearyl Glycyrhethinate, Retinyl Palmitate, Glycerin, Glyceryl Polyacrylate, Dimethicone, Cetyl Alcohol, Cetearyl Alcohol, Cetareth-20, Caprylyl Methicone, Carbomer, Tromethamine, Disodium EDTA, Potassium Sorbate, Phenoxyethanol, Ethylhexylglycerin, Parfum/Fragrance

SkinMedica Essential Defense Mineral Shield Broad Spectrum SPF 35 Sunscreen: Water, Cyclopentasiloxane, Dimethicone, Polyglyceryl-3 Polydimethylsiloxyethyl Dimethicone, Butylene Glycol, Aluminum Hydroxide, Dimethicone/PEG-10/15 Crosspolymer, PEG-9 Polydimethylsiloxyethyl Dimethicone, Sodium Chloride, Caffeine, Camellia oleifera Leaf Extract, Sodium Citrate, Dimethicone/Vinyl Dimethicone Crosspolymer, Triethoxysilylethyl Polydimethylsiloxyethyl Hexyl Dimethicone, Stearic Acid, Ethylhexylglycerin, Phenoxyethanol

Test Product B (4% Hydroquinone Topical Prescription Cream):  
[Ingredients TBD depending on Pharmacy]

#### **4.2 Subject Compliance**

[figure not shown]
Subject compliance to the study treatment regimen will be verbally assessed; study personnel will ask each subject whether they missed any applications of study treatment since the previous visit and will quantify the subject's response.

[figure not shown]
#### **4.3 Concomitant Medications**

Systemic and topical medications being used at baseline that are considered necessary for the subject's welfare and will not interfere with the study may be used. Administration of these drugs must be reported on the appropriate case report form and any alterations in the use of the medication during the study will be carefully noted. Administration of a prohibited drug (*see section 4.2 of protocol*) in an emergency situation is done with the safety of the study participant as the prime consideration. All topical and systemic medications that the subject receives during the study will be recorded. Any alterations will be noted.

#### **4.4 Treatment Group Randomization**

Subjects will be randomized in a 1:1 fashion to receive treatment with SkinMedica's cosmetic topical brightener or 4% hydroquinone. A randomization table will be provided by the sponsor and used to determine which facial side will be treated with Test Product A (cosmetic topical serum "Lytera 2.0") and Test Product B (4% hydroquinone) for each subject.

- Randomization and distribution of study products by the Unblinded study staff

[REDACTED]

## 6.0 ASSESSMENTS

### 6.1 Clinical Grading of Efficacy Parameters

Clinical grading of the efficacy parameter will be performed at the study visits indicated. Hyperpigmentation will be assessed on **the left and the right side** of each subject's face separately.

#### **Melasma Severity Rating Scale:**

At the screening/baseline visit and the end of treatment visit (week 12), the Investigator will assess the subject's facial skin for the severity of symmetrical facial melasma using the following Melasma Severity Rating Scale on the left and right facial sides. Subjects must present with a score of 2 for the left and the right facial sides to be enrolled into the study.

Score	Hyperpigmentation Status
0	Cleared: color of melasma lesions approximately equivalent to surrounding normal skin or with minimal residual hyperpigmentation
1	Mild: color slightly darker than the surrounding normal skin
2	Moderate: color moderately darker than the surrounding normal skin
3	Severe: color markedly darker than the surrounding normal skin

**Overall Hyperpigmentation Scale:**

At all visits (baseline, weeks 4, 8 and 12), the Investigator will globally assess the subject's left and right facial sides for overall hyperpigmentation using the following ten point scale (0 – 9):

None (Score of 0)	Skin is normal in color with no evidence of hyperpigmentation
Mild (Score of 1, 2 or 3)	Several brown spots with increased pigmentation; they are small in size and slightly darker than surrounding skin
Moderate (Score of 4, 5 or 6)	Many brown spots with increased pigmentation; they are medium in size and much darker than surrounding skin
Severe (Score of 7, 8 or 9)	Many large brown spots with increased pigmentation; they are large in size and markedly darker than surrounding skin

